Safety and Efficacy of Hyperosmolar Saline Irrigation Fluid in Arthroscopic Knee Surgery

IRB Project #: 2011296

PROTOCOL VERSION NUMBER: 3.0

DATE: 03 APR 2019

Principal Investigator: [name]

Co-Investigators: [name], DVM, PHD; [name]; [name]

Study Sites: University of Missouri Health System

TABLE OF CONTENTS

1. Background Information & Significance
2. Objectives, Contribution, & Hypothesis
3. Selection of Subjects
4. Study Procedure
5. Confidentiality of Data
6. Assessment of Risks & Benefits
7. Payment and Remuneration, and Costs
8. References

1. Background Information & Significance

An isotonic solution, such as saline (0.9%, 300mOsm/L) or lactated ringer's (273 mOsm/L), is commonly used and safely proven for joint irrigation during arthroscopy. Arthroscopic fluid is usually pressurized to enable visualization through dilation of the joint or bursa and prevent bleeding from the microvasculature. It has been recommended that this pressure be maintained at 49mmHg or less below the systolic blood pressure to preserve the clarity of view. The combination of large amounts of pressurized irrigation solution and lengthy arthroscopic procedures may cause substantial tissue fluid retention. Thus, extravasation of irrigation fluid into the periarticular tissues is inevitable and may create technical difficulties as well as patient morbidity and complications. Previous investigators have reported complications including tracheal obstruction, post-operative airway edema and compromise leading to prolonged intubation, excess weight gain, neurologic injuries, skin necrosis, and fluid overload associated with excessive fluid extravasation and tissue retention. Furthermore, it has been shown that fluid accumulated during the operation is slowly released back into the systemic circulation. Although there is not a rapid change in circulating volume, there may be implications for elderly patients and those with multiple comorbidities during prolonged arthroscopic surgery. Our research team and other groups have reported that hyperosmolar solutions (up to 600 mOsm/L) are chondroprotective *in vitro*, and safe and effective clinically when used as the irrigation solution for arthroscopic shoulder surgeries in a prospective controlled randomized clinical trial.

2. Objectives, Contribution, & Hypothesis

Objectives: To determine if a hyperosmolar solution, similar to what is used in head trauma patients, can reduce the degree of fluid extravasation in knee arthroscopy. To determine if a hyperosmolar solution has any effect on post-operative knee pain compared to the standard isotonic solution. To determine if a hyperosmolar solution has any effect on post-operative pain medicine consumption compared to the standard isotonic solution.

Contribution: The potential benefits of this study lie in determining the differences noted in our shoulder arthroscopy clinical trial extend to arthroscopic knee procedures.

Hypothesis: A hyperosmolar irrigation solution used in knee arthroscopy will reduce the extent of fluid extravasation to surrounding tissue, decrease perioperative pain, and result in diminished utilization of perioperative pain medication.

3. Selection of Subjects

Inclusion Criteria: Adult patients (18 years of age or greater) undergoing arthroscopic knee surgery who are willing and able to consent.

Exclusion Criteria: Current pregnancy or breastfeeding; Unable to give consent; Prisoner; Mentally Disabled.

Sample Size: We anticipate enrolling up to 100 patients to complete the study. Patients will be evenly randomized to either hyperosmolar or standard irrigation solution.

4. Study Procedure

Timeline: 12-24 months of data collection

Protocol: Study candidates will be identified as they present to the clinic at the Missouri Orthopaedic Institute at the University of Missouri, and will be evaluated by one of our three sports orthopaedic surgeon co-investigators. Informed consent will be obtained as per IRB protocol. Enrollees will receive a copy of the study protocol, consent, and HIPAA form. Background patient information will be collected including age, sex, BMI and co-morbidities. American Society of Anesthesiologist (ASA) classification will be assigned by the involved anesthesiologist.

Lactate Ringer's (LR, 273mOsm/L) is commonly used at our facility as our isotonic standard irrigation solution and will serve as the control to be evaluated against a hyperosmolar (1.9%, 600mOsm) solution. The hyperosmolar solution will be created by adding 120cc of 23.4% NS solution to a 3L bag of LR. The patient will be randomized before surgery by a research team member by obtaining a sealed envelope that designates the type of irrigation solution to be used in the surgery. If randomized to the hyperosmolar group, an OR staff member will make the solution prior to the start of the case. The surgeon and patient will be blinded to the type of irrigation solution used in surgery.

Quantitative variables that will be recorded include, pre and post-operative blood pressure, the type and amount (mL) of irrigation fluid used, amount of intravenous fluid used (mL), pre and post-operative weight (lb), procedures performed, number of portals, arthroscopic surgical time (minutes), pre and post-operative knee girth measurements (cm), and amount of perioperative opioid medication. We will also document any immediate, post-operative adverse effects (ie, airway comprise, prolonged intubation, etc.).

Weight: On the day of surgery, the patient's weight will be measured to the closest one tenth of a pound (lb) before and after surgery on the same calibrated, digital weighing scale. Patients will be weighed while wearing the same attire and hospital gown for each measurement. After surgery, patients will be weighed before discharge and before voiding or eating to ensure that the maximal amount of weight gain attributable to shoulder arthroscopy can be documented. A standard amount of dressing will be applied for each procedure that is surgeon specific and will be accounted for during the calculation of weight gain. Intraoperatively, we will record the

amount of intravenous fluid given during the case (mL).

Knee Girth: Change in knee size (girth) will be evaluated based on change in surface area. Prior to start of the surgery, a sterile measuring tape will be used to record knee girth. Following the surgical procedure the operating surgeon will perform a repeat measuring of the knee girth. During the assessment, the patients will lay supine with the tester aiming to maintain the hip in neutral position. The knee will be relaxed and extended as much as possible. If the knee extends below 0°, a cylinder firm back roll will be placed under the heel of the foot. The tester will stand closest to the examined leg and place a small dot with a pen 1 cm proximal to the base of the patella using a non-elastic tape measure. The mark will be removed between measurements. The tape measure will be placed carefully and snug above the dot, and the tester will measured the knee joint circumference. The tape measure will be blinded on the side facing the tester. When the tester is satisfied with the alignment of the tape measure, the unblinded scale will be revealed to the data recorder. The value will be recorded to the nearest 0.1 cm and the measurement will be repeated. The highest value of the two knee circumference recordings will be used in the data analysis

Prior to departure from the hospital, the patient will be given the option to either receive a paper copy of the Pain Evaluation form or have an electronic version sent to them (through Patient IQ) each day. The patient will be instructed to write down their pain level (based on the Visual Analog Score, 0-10) and amount of pain medication taken during each day from the day of surgery to post-operative day 3. If given the paper form, the patient will return this form at his/her first post-operative clinic visit.

Approximately 1 year after surgery, patients will be contacted via telephone by a member of the research team. A telephone questionnaire will be conducted to gain additional information about their recovery and current functional status. The phone interview will include questions pertaining to three outcome measures: 1) KOOS Jr, 2) Single Assessment Numeric Evaluation (SANE) score for their knee, and 3) Data collection regarding any additional surgeries involving the affected shoulder.

5. Confidentiality of Data

Patient confidentiality during the course of this study will be protected in compliance with HIPAA requirements as well as the requirements of the University of Missouri Health-Sciences IRB.

All subjects will be assigned a study identification number that requires the use of a key in order to decipher a subject's personal identification information. The key will be kept in the Cerner Power Trials database, which is password protected. The study identification number will be used to label all paper data collection instruments.

All subject information in electronic format will be kept in password-protected storage. All subject information in paper format will be kept in locked cabinets in a secured suite at the

Missouri Orthopedic Institute, and otherwise will be archived in a secure storage facility, or destroyed.

6. Assessment of Risks & Benefits

Risks: Risks for breach of confidentiality does exist but will be limited with tight control and limited access to the investigators.

Benefits: The potential benefits of this study lie in determining the differences noted in our shoulder arthroscopy clinical trial extend to arthroscopic knee procedures.

Data Safety Monitoring Plan: Subject safety will be ensured through standard of care perioperative monitoring by the anesthesia staff.

7. Payment and Remuneration, and Costs

Payment and Remuneration: Participants will not receive payment for participating in this study.

Costs: Subjects will be responsible for the cost of any surgical and clinic follow up costs. The treatment arm does not in any way effect the costs that patients are experiencing.

8. References

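### No pre-operative measure of knee pain, habitual analgesic use, KOOS Jr or SANE is specified, which costs precision and interpretability but does not bias the comparison

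*Protocol*

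**What the plan says.** All of the measurement schedule is in Section 4 (Study Procedure) of the protocol.

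- **Background data:** "Background patient information will be collected including age, sex, BMI and co-morbidities". ASA class follows in the next sentence.
- **Recorded variables:** blood pressure and weight are taken before and after surgery, and the list ends with "pre and post-operative knee girth measurements (cm), and amount of perioperative opioid medication".
- **Pain and medication:** "Prior to departure from the hospital, the patient will be given the option to either receive a paper copy of the Pain Evaluation form", or else an electronic version. On it the patient writes a 0-10 pain score and the "amount of pain medication taken during each day from the day of surgery to post-operative day 3".
- **Function:** "Approximately 1 year after surgery, patients will be contacted via telephone by a member of the research team". "The phone interview will include questions pertaining to three outcome measures: 1) KOOS Jr, 2) Single Assessment Numeric Evaluation (SANE) score for their knee"; the third item is further surgery. The stated purpose is: "A telephone questionnaire will be conducted to gain additional information about their recovery and current functional status".

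Section 2 has three objectives: fluid extravasation, pain and pain-medicine consumption. The pain objective reads "To determine if a hyperosmolar solution has any effect on post-operative knee pain compared to the standard isotonic solution". Section 3 admits any consenting adult having knee arthroscopy, and none of its exclusions concerns existing knee pain or regular opioid use.

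**The concern.** The protocol plans a before-and-after pair for its extravasation measures (weight and girth) but not for the outcomes of its other two objectives or for its 1-year scores. With entry this broad, patients may start from very different levels of pain, analgesic use and function. A regular opioid user and an opioid-free patient enter the same day 0 to 3 medication comparison, and no specified item records prior use.

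This belongs to the protocol rather than to an analysis plan. An analysis plan decides how data are used; it cannot recover a pre-operative value that nobody was told to collect.

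At stake are the precision of the pain and medication comparisons, the ability to examine or adjust for chance imbalance in these measures, and the ability to describe the 1-year scores as change from the patient's starting state.

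**Working it through.** **Is a baseline specified?** Going through Section 4 for each outcome:

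| Outcome | Pre-operative value specified | Post-operative value |
|---|---|---|
| Weight, girth, blood pressure | yes | yes |
| Knee pain, 0-10 | no | day 0 to day 3 |
| Pain medication | no habitual use; the perioperative opioid amount may include same-day dosing | day 0 to day 3 |
| KOOS Jr, SANE | no | about 1 year |

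**What could a baseline add?** The protocol gives no alpha, power, effect size, SD or correlation, so there is no figure of its own to reproduce. What follows is illustration.

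*From the protocol:* up to 100 patients, evenly randomised, so about n = 50 per arm.

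*Assumed:* baseline-outcome correlation r of 0.3, 0.5 or 0.7; two-sided alpha 0.05; 80% power for the detectable difference; a true effect of 0.5 SD for the power column.

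*Formulas:*
- Residual variance factor after adjustment = 1 − r².
- Unadjusted detectable difference = (1.960 + 0.842) × √(2/50) = 2.802 × 0.20 = 0.56 SD. Adjusted: multiply by √(1 − r²).
- Equivalent unadjusted n per arm = 50 / (1 − r²).

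| r | 1 − r² | Detectable difference (SD) | Power at 0.5 SD | Equivalent n per arm |
|---|---|---|---|---|
| no adjustment | 1 | 0.56 | 70.5% | 50 |
| 0.3 | 0.91 | 0.535 | 74.6% | 55 |
| 0.5 | 0.75 | 0.485 | 82.3% | 67 |
| 0.7 | 0.51 | 0.40 | 93.8% | 98 |

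Put the other way, at r = 0.5 a trial of 100 without the baseline has about the precision of 100 × 0.75 = 75 patients with it.

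**How large might a chance imbalance be?** The standard error of a between-arm difference in a baseline measure is √(2/50) = 0.20 SD. An imbalance above 0.3 SD in either direction (0.3 / 0.20 = 1.5 standard errors) has probability 13.4%. With an assumed 40 evaluable patients per arm it is 18.0%. An imbalance of 0.3 SD would move the observed outcome difference by 0.3 × r, that is 0.09 SD at r = 0.3 and 0.21 SD at r = 0.7. The unadjusted standard error already allows for such shifts. Without the baseline, however, one cannot see whether a shift occurred in this trial, or remove it.

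**The case against.** The strongest reply is that allocation is randomised. The unadjusted comparison is unbiased, and its confidence interval already covers chance differences in every unmeasured characteristic. That stands. A reader might infer from the missing baselines that a 1-year difference could not be told apart from a difference present at entry, as in an observational study. The protocol does not support that reading, because patients are assigned by sealed envelope.

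Nor do the objectives need change scores. They ask for post-operative levels compared between arms, and those can be answered as the protocol stands. KOOS Jr and SANE serve none of the three objectives, and the protocol promises no change from baseline. That also stands. The narrower point is that a single score, collected partly to learn about recovery, describes status only.

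It would also go too far to say that these measures are never taken or that nothing distinguishes the patients. The background list is introduced by a word that leaves it open, and co-morbidities, ASA class and the procedures performed are recorded. The supportable statement is that no pre-operative measure is specified. An item that nobody is instructed to collect cannot be counted on to exist uniformly, and same-day opioid dosing does not show habitual use.

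Finally, the size rests on an assumed correlation, and one value need not suit every outcome. Clinic-visit knee pain may predict acute surgical pain only weakly. The factor 1 − r² also measures the gain over a model with no covariates at all; beyond age, BMI, ASA class and procedure the gain could be smaller. This limits the claimed benefit without removing it.

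**Conclusion.** The point holds as a loss of precision and interpretability on two of the three objectives and on the 1-year scores. It is not a threat to validity, and it is best treated as a cheap improvement.

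Under assumed correlations of 0.3 to 0.7, adjustment would cut the residual variance by 9% to 49%. The lower figure is a sensible planning value for day 0 to 3 pain. The documents supply no correlation, so the range is illustrative, and the power figures rest on the further assumptions listed with the calculation. That no such pre-operative measure is specified, and that no later analysis could recover one, rests on the text alone.

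**What to change.** Add one short form to Section 4, completed before the randomisation envelope is opened, either at the enrolment visit or on the day of surgery. It should hold the same 0-10 knee pain rating, KOOS Jr, SANE, and recent analgesic and opioid use (type and amount over a stated recall period). Choose one time point for all patients and record the date, since the protocol does not say how long before surgery enrolment takes place. List these items with the background data, and name each as the covariate for its own post-operative outcome, in the analysis plan if there is one.

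The cost is a few minutes of each patient's time and a minor amendment. The form reuses the trial's own instruments at a contact that already takes place, and adds no patients or procedures. Patients already operated on will lack these baselines, so the earlier the form is introduced the more it yields. The analysis should say how those missing values are handled.

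### Fluid is mixed in one arm only and blinding is stated only for surgeon and patient, so nothing keeps staff who give or record in-hospital opioid from learning the arm

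*Protocol*

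**What the plan says.** All the relevant conduct text is in Section 4, Study Procedure, of the protocol.

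- **Allocation.** Before surgery a research team member randomizes the patient by "obtaining a sealed envelope that designates the type of irrigation solution to be used in the surgery".
- **Preparation.** The hyperosmolar fluid is made by adding concentrated saline to a 3 L bag of lactated Ringer's. On who does this and when: "If randomized to the hyperosmolar group, an OR staff member will make the solution prior to the start of the case". No step is given for control bags, and no cover, code or neutral label for either arm.
- **Blinding.** "The surgeon and patient will be blinded to the type of irrigation solution used in surgery". No other role is named.
- **Recorded variables.** The list includes "the type and amount (mL) of irrigation fluid used" and, at its end, "and amount of perioperative opioid medication". The protocol does not say who gives or who records the opioid.

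Section 2 gives pain medication two wordings. One objective asks whether the hyperosmolar solution "has any effect on post-operative pain medicine consumption compared to the standard isotonic solution". The hypothesis is directional and says the solution will "result in diminished utilization of perioperative pain medication". Section 6 assigns perioperative safety monitoring to the anesthesia staff, who are not among the roles stated as blinded.

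**The concern.** How much opioid a patient receives in hospital depends partly on the judgement of the people giving it. If they know the arm, and the study expects less opioid in one arm, the amount given or written down can drift in the expected direction without any effect of the fluid. A difference in that variable could then not be attributed cleanly to the irrigation solution.

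A preparation step carried out in one arm only is a natural way for the arm to become known. The protocol sets out that step and describes nothing that would hide it from staff other than the surgeon and the patient.

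**Working it through.** The plan gives no figure to reproduce here, so the check sets the statements side by side.

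**1. Who could learn the arm.** Two roles handle the allocation: the research team member who obtains the envelope and the OR staff member who mixes. Two roles are stated as blinded: surgeon and patient. Anesthesia staff, recovery staff and those who record data are in neither group. The protocol does not say that they are told the arm, and it does not say that they are kept from it.

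**2. What the mixing step reveals.** Section 3 says: "Patients will be evenly randomized to either hyperosmolar or standard irrigation solution". With up to 100 patients, 100 / 2 = about 50 cases have a mixing step and about 50 have none. For someone placed to know whether a mix was made, its presence points to one arm and its absence to the other, so the signal covers both groups.

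**3. Which outcomes are exposed.**

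| Outcome | Who produces it | Protection in the text |
|---|---|---|
| Knee girth after surgery | Operating surgeon | Stated as blinded; tape scale hidden from the tester |
| Weight | Digital scale, read to 0.1 lb | Objective reading |
| Pain score and medication, day of surgery to day 3 | Patient | Stated as blinded |
| In-hospital opioid amount | Not stated | None stated |

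The gap falls mainly on the last row. The amount of intravenous fluid is also at staff discretion, but it is recorded, so an imbalance could be seen.

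**4. Does the patient's record stand in for the in-hospital amount?** It has 4 daily entries (day of surgery plus days 1, 2 and 3) and serves the objective on post-operative consumption. It does not fully replace the in-hospital amount. The form is offered only before the patient leaves the hospital, and a patient cannot log what was given during surgery (my inference). Of the two measures of pain medication, one is therefore blinded and one has no stated blinding.

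**5. Size.** The protocol gives no variability, effect size or significance level for opioid use, and nothing from which to judge how far staff behaviour might shift. Any false-positive rate would depend entirely on an assumed shift, so none is given.

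**The case against.** The strongest reply is that silence is not unblinding. The protocol commits to a blinded surgeon, who works beside the fluid throughout the case. Keeping that commitment may require hiding the bag, and this could hide it from anesthesia staff as well. Mixing is done before the case starts, and no route to recovery staff is shown. A reader might infer from the text that anesthesia or recovery staff do know the arm, or that the opioid comparison is biased. The documents support neither inference. What stands against the reply is that the protocol is not merely silent. It lists who is blinded and describes a one-arm step, so it can be followed to the letter with staff fully aware of the arm.

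Three further objections have merit.

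- The word perioperative in the hypothesis is not defined. The same sentence uses it of pain, and the only pain score is the patient's record to day 3, so the medication hypothesis may include or mean that record. The link to in-hospital opioid is possible but not certain.
- Fluid type and opioid amount stand in one list of variables, but a list is not a data form. It does not show that one person records both, and every trial must record the treatment received.
- Leaving anesthesia staff unblinded can be defended, because their monitoring is the stated safety measure. That calls for an unblinding route, or for a plain statement that they are not blinded.

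The unseen SAP does not answer the point. Who prepares the bags and who is blinded is settled before each case, and an analysis plan cannot restore masking afterwards.

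**Conclusion.** The point holds as a cheap improvement that should be made. It is not a flaw that undoes the trial. As written, Section 4 leaves staff who give or record in-hospital opioid unprotected from learning the arm, through a preparation step that exists in about 50 of up to 100 cases. The consequence is confined mainly to one recorded variable. Girth, weight and pain are largely protected, and the objective on post-operative consumption keeps a blinded measure.

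This rests on two assumptions: that some of the staff concerned are placed to see or hear of the mixing, and that the in-hospital amount is meant to bear on the hypothesis. Neither is stated. A reader might go further and conclude that the whole pain-medication question is compromised. The patient's blinded record speaks against that.

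**What to change.** Amend Section 4 as follows.

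1. Existing staff who do not give or record that patient's opioid prepare the bags for both arms in the same way, out of view of the operating and anesthesia team, with enough bags for the case. Fluid composition does not change.
2. Label the bags only with the study number, which Section 5 already uses on paper data forms.
3. Keep fluid type in a separate log, off the form used by those who record outcomes.
4. State that staff who give or record opioid are blinded, and give a route to unblind for safety.

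If this is not practicable, state that in-hospital opioid is an unblinded measure and rest the pain-medication conclusion on the patient's record from the day of surgery to day 3. Either way, define which measure the hypothesis means by perioperative pain medication.

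The cost is labels, a separate log, some reassignment of bag handling (now split between a research team member and an OR staff member) and an unblinding route. No extra patients, visits or measurements are needed.

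### The title names safety, but adverse events are collected only in the immediate post-operative period and no later planned contact asks about them

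*Protocol*

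**What the plan says.** The title is "Safety and Efficacy of Hyperosmolar Saline Irrigation Fluid in Arthroscopic Knee Surgery". None of the three objectives in Section 2, nor the hypothesis, concerns safety.

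Section 4 contains the only rule for collecting adverse events: "We will also document any immediate, post-operative adverse effects (ie, airway comprise, prolonged intubation, etc". The Data Safety Monitoring Plan in Section 6 says: "Subject safety will be ensured through standard of care perioperative monitoring by the anesthesia staff".

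Section 4 also plans three later contacts:

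- A daily form, on paper or electronic, for a pain score and the "amount of pain medication taken during each day from the day of surgery to post-operative day 3".
- The first post-operative clinic visit, mentioned only for collecting the paper form: "the patient will return this form at his/her first post-operative clinic visit".
- A telephone call at about one year, covering KOOS Jr, SANE and additional surgeries. The surgery item names the shoulder, although this is a knee trial.

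The Background (Section 1) states that "fluid accumulated during the operation is slowly released back into the systemic circulation" and that, although circulating volume does not change rapidly, "there may be implications for elderly patients and those with multiple comorbidities during prolonged arthroscopic surgery". Section 3 admits adults with no upper age limit and no exclusion for comorbidity.

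**The concern.** The collection rule carries a time limit. It is a stated choice and not a gap that a statistical analysis plan could fill, because an analysis plan can only work on events that were collected. The limit sits badly beside the Background, whose one statement about timing describes a process that continues after the operation and may matter for patients whom the trial admits.

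At stake is what the trial may say about safety. If few or no events are recorded, the report could present this as evidence of safety under a title that promises it. It would be evidence only for the immediate post-operative period, since nobody is asked about adverse events afterwards.

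**Working it through.** The protocol gives no event rate, no share of events by time and no safety target, so there is no figure to reproduce. The main check is a comparison of each planned contact with what it collects.

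| Contact | Collected | Adverse-event question? |
|---|---|---|
| Perioperative, immediate | Weight, girth and blood pressure before and after surgery; immediate adverse effects | Yes |
| Day 0 to 3 form | Pain score, pain medication | No |
| First clinic visit | Return of the paper form | None stated |
| Call at about one year | KOOS Jr, SANE, additional surgeries | No |

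The adverse-event record therefore stops at the first row.

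**What zero recorded events would mean.** Up to 100 patients are randomized evenly, so 100/2 = 50 per arm. If 0 of 50 have a recorded event, the exact one-sided 95% upper limit is 1 − 0.05^(1/50) = 5.8%. That limit applies to events inside the recording window. It puts no bound on later events, at any sample size.

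**Illustration of the loss.** Let p be the true event rate and f the share of events arising after the window. Both are assumptions; the protocol gives neither. The probability of recording no event among 50 patients is (1 − p(1 − f))^50.

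| | f = 0 | f = 0.5 | f = 0.8 |
|---|---|---|---|
| p = 0.10 | 0.90^50 = 0.5% | 0.95^50 = 7.7% | 0.98^50 = 36.4% |
| p = 0.05 | 0.95^50 = 7.7% | 0.975^50 = 28.2% | 0.99^50 = 60.5% |

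The f = 0 column is full capture. If almost no events arise late, the window costs almost nothing. The table shows how the loss grows with f; it does not estimate f.

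**The case against.** The strongest reply is that the mismatch in timing is less sharp than it looks. The Background gives no hours or days for the slow release and ties its possible implications to prolonged surgery, while Section 4 does not say when the immediate period ends. It also presents the harms of fluid retention as a problem of irrigation in general, which the study solution is hypothesised to reduce. Missed late fluid events could therefore understate a benefit as easily as hide a harm. All of this stands. It removes any claim about the direction of bias, but it does not create an adverse-event question after the immediate period.

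Three stronger readings are tempting, and the protocol does not support them:

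- **That only airway events are recorded.** The rule covers any adverse effect and its examples are open-ended, so no event type is excluded. The defect is the time limit.
- **That the Background describes neurologic injury or skin necrosis as delayed.** It lists "excess weight gain, neurologic injuries, skin necrosis, and fluid overload associated with excessive fluid extravasation and tissue retention" among reported complications without giving any onset time. Only the slow release of fluid has a time element.
- **That the trial is blind to everything later.** Weight, girth and blood pressure after surgery capture early retention; pain and medication run to day 3; and the one-year call may pick up re-operation or poor function indirectly. None of these is adverse-event collection, but together they rule out a claim of complete blindness.

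It can also be said that no objective concerns safety and no safety test is planned. That lowers the weight of the point. It also means that the word in the title has no matching collection behind it.

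**Conclusion.** The point holds as a cheap improvement and not as a serious flaw. The protocol fixes adverse-event collection to the immediate post-operative period, supports it only with perioperative monitoring, and asks no adverse-event question at any later planned contact. Later events in either arm would go unrecorded as adverse events, and a low count could not support a safety statement beyond the immediate period.

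This conclusion rests on the protocol's text alone. The zero-event probabilities are illustration: the rates of 5% and 10% and the late shares of 50% and 80% are assumptions, and a late share near zero would remove the effect. The 5.8% limit reflects sample size and not the window.

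**What to change.** In Section 4, replace the restriction to immediate effects with recording from surgery through the first post-operative clinic visit:

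- Add one adverse-event item to the day 0 to 3 form, in both the paper and electronic versions.
- Add one adverse-event check at the first clinic visit. The protocol does not say when this visit falls, so record its date so that the length of observation is known.
- Report adverse-event counts by arm.

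If the collection rule is left as it is, limit any safety statement to the immediate post-operative period.

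The cost is slightly more data entry. The form and the visit are already planned, so no new visit or test is needed, and treatment is unchanged.
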